A Study Protocol for a Randomised Controlled Trial Evaluating the Benefits from Bimodal Solution with Cochlear Implant and Hearing Aid vs. Bilateral Hearing Aids in Patients with Asymmetric Speech Identification Scores.

Trial Registration Number: NCT04919928 (ClinicalTrials.gov)

Updated: 21.08.22

Statistical analysis plan (SAP) for randomised clinical studies.

Project responsible
Consultant [name] and Ph.D. student [name]
Title
A Study Protocol for a Randomised Controlled Trial Evaluating the Benefits from Bimodal Solution with Cochlear Implant and Hearing Aids vs. Bilateral Hearing Aids in Patients with Asymmetric Speech Identification Scores.
Deadline
30.07.2024
Study design
Randomised controlled trial
Samplesize
60 participants
Aim
This randomised controlled trial is designed to improve clinical decision-making for CI candidacy for patients with asymmetric hearing. It is necessary to establish more evidence to support the effectiveness and the fitting optimization of bimodal CI+HA versus HAs in patients with asymmetric hearing.

The first objective of the study is to evaluate the subjective (SSQ12) and objective (Hearing In Noise Test (HINT) which is word and sentence based and DANTALE I, which is monosyllabic word-based) benefits of a bimodal solution (CI+HA) compared to (HA+HA). The second objective is to compare and evaluate patient self-reported outcomes with NCIQ, THI and DHI in the intervention group (CI+HA) with the control group (HA+HA). The third objective is to evaluate if listening effort, hypothesized to cause fatigue, can be measured objectively by HINT with pupillometry. To minimize listening effort and optimize the fitting of bimodal solution the CI fitting and loudness balancing on individual level will be evaluated.

Hypothesis

Patients treated with a CI on the poorer hearing ear and a HA to the better hearing ear (CI+HA) in a bimodal solution have increased objective and subjective measured speech intelligibility compared to patients treated with new bilateral replacement hearing aids (HA+HA).

2) Data description

See Appendix A

3) The statistical analysis plan (SAP)

Definition of outcome

Primary Outcome

Primary outcomes are Speech intelligibility scores measured objectively with HINT (sentences and words) and DANTALE I and subjectively with Speech, Spatial and Qualities of Hearing scale (SSQ-12).

Secondary Outcome

Patient reported outcomes scores assessed with the Nijmegen Cochlear Implant Questionnaire (NCIQ), The Tinnitus Handicap Inventory (THI) and Dizziness Handicap Inventory (DHI).

Third Outcome

Listening effort assessed with pupil dilation with HINT.

Definition of treatment variables

Treatments are HAs and CI-surgery assigned by randomisation. The primary comparison will be between the CI+HA and HA+HA groups.

Covariates used in analyses

Stratified randomisation for thresholds of the ear to be implanted.

Definition of effect size/parameter of interest

Primary effect size:

Objective outcome: Mean difference in HINT in quiet and in noise between intervention group (HA+CI) and control group (HA+HA) at 3, 6 and 12 months follow-up post- bimodal CI+HA-fitting and 3 months post-HA-fitting respectively.

Subjective outcome: Mean difference in SSQ-12-scores at 3, 6 and 12 months follow-up post- bimodal CI+HA-fitting and 3 months post-HA-fitting respectively

Definition of Analysis Sets

Strategy for intention to treat analysis with incomplete observations.1)

1. Attempt to follow-up on all randomised participants, even if they withdraw from allocated treatment.
2. Perform a main analysis of all observed data that are valid under a plausible assumption about the missing data.
3. Perform sensitivity analyses to explore the effect of deviations from the assumption made in the main analysis.
4. Account for all randomised participants, at least in the sensitivity analyses.

1)

White, Ian R., Nicholas J. Horton, James Carpenter, and Stuart J. Pocock. 2011. 'Strategy for Intention to Treat Analysis in Randomised Trials with Missing Outcome Data'. *BMJ* 342 (February): d40. <https://doi.org/10.1136/bmj.d40>.

Analysis specification

A constrained linear mixed model is used to analyse the outcome.

The model will include randomisation group (CI+HA / HA+HA) and time (baseline/follow-up) and their interaction as fixed effects along with the threshold strata that were used in stratifying the randomisation. The model is constrained so that the mean at baseline agrees

across the two treatment groups adjusted for threshold stratum, which is reasonable due to the randomisation of implant fitting. Patient ID will be included as a random effect to account for the repeated measurements.

Secondary outcomes will be analysed analogously in a constrained linear mixed model adjusting for randomisation strata. Model validation checks will be undertaken as described above, switching to bootstrapping the standard errors when model assumptions are rejected. Covariates such as age and gender will be included in all models.

Sensitivity analysis

Inclusion is performed conditional on Pure Tone Average (PTA) (from 0.5 to 4 kHz) PTA > 40 dB HL and SIS <50% in the ear considered for CI implantation and <70% in the best-aided condition which may lead to a truncation effect in the distribution of baseline measurements.

To address this, an analysis of covariance (ANCOVA) model conditioning on the baseline will be used to obtain a sensitivity analysis estimate for the main outcome. (2)

The statistical analysis plan is attached as “supplementary file” along with the Data Description listed in Appendix A.

2)

Liu, Guanghan F., Kaifeng Lu, Robin Mogg, Madhuja Mallick, and Devan V. Mehrotra. 'Should Baseline Be a Covariate or Dependent Variable in Analyses of Change from Baseline in Clinical Trials?: ANALYSES OF CHANGE FROM BASELINE IN CLINICAL TRIALS'. *Statistics in Medicine* 28, no. 20 (10 September 2009): 2509–30. <https://doi.org/10.1002/sim.3639>.

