The primary outcome measures are Speech intelligibility measured objectively with HINT (sentences in noise) and DANTALE I (words) and subjectively with the Speech, Spatial and Qualities of Hearing scale questionnaire (SSQ-12). Secondary outcomes are patient reported Health-Related Quality of Life (HRQoL) scores assessed with the Nijmegen Cochlear Implant Questionnaire (NCIQ), the Tinnitus Handicap Inventory (THI) and Dizziness Handicap Inventory (DHI). Third outcome is listening effort assessed with pupil dilation during HINT

In conclusion, the purpose is to improve clinical decision-making for CI candidacy and optimize bimodal solutions.

Ethics and Dissemination

This study protocol was approved by the Ethics Committee Southern Denmark project ID S-20200074G. All participants are required to sign an informed consent form.

This study will be published upon completion in a peer-reviewed publications and scientific conferences.

Trial Registration Number: NCT04919928 (ClinicalTrials.gov)

Strengths and Limitations of This Study

- The study uses comprehensive measures of self-reported outcomes as well as objective tests of speech intelligibility.
- Listening effort controlled with pupillometry during objective tests of speech intelligibility.
- Open label RCT (blinding is not possible due to visibility of the CI).
- Possible large drop rates if new HAs improve speech intelligibility to an extent that CI treatment is rejected or postponed.

Introduction

Background

Cochlear implants (CIs) have been used to restore hearing in individuals with severe to profound sensorineural hearing loss. Initially, most patients receiving a cochlear implant were profoundly deaf in both ears. (1, 2) However, recently it has become more common to implant patients with significant residual hearing in the affected ear, as well as in patients with asymmetric hearing loss and single-sided deafness, with significant residual hearing or normal hearing on the contralateral side.(3, 4) A CI in one ear and a HA in the other ear can provide enhanced hearing performance in patients with asymmetrical hearing.(5, 6) The combination of CI and HA is referred to as bimodal hearing or bimodal solution.(7)

CI Candidacy

In the UK, The National Institute for Health and Care Excellence (NICE) have listed guidelines for cochlear implantation and recommends that unilateral CI is offered to patients

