The training focuses on learning to identify different sounds from the environment and word discrimination.

The new CI will also be prescribed to the patients free of charge and future service will be free of charge as well.

Loudness Balancing

At 3- months follow-up the post-surgery complications will be evaluated and the levels in the CI will be adjusted if necessary.

In the loudness balancing procedure, the patient will have both the hearing aid and CI activated and at the 6-month follow-up, when the CI mapping levels are stable, patients will be randomised and assigned to one of three bimodal fitting groups:

Group A) will not complete any specific loudness balancing procedures, CI and HA will be fitted based on individual feedback from the patient.

Group B) will be fitted/finetuned using a bimodal loudness balancing task at a medium input level and adjusted based on the patient feedback. The audiologist will present a mid-level sound (approx. 55dB SPL (sound pressure level)) at the center-speaker.

Group C) will be fitted/finetuned using a bimodal loudness balancing task as group B but the audiologist will play three levels and adjust the gain for three input levels (soft, medium, and loud) according to the patient feedback.

For both groups B and C, the patient will be given a 'Bimodal Fusion' illustration (see Figure 3) and asked to provide feedback about the location of the sound by tracing over the line of

the head. The HA gain will be adjusted using the bimodal adjustment option until the patient reports that the sounds are perceived at the center of the head.(24)

Primary Outcome

Primary outcomes are Speech intelligibility scores measured objectively with HINT (sentences and words) and DANTALE I and subjectively with Speech, Spatial and Qualities of Hearing scale (SSQ-12). (9, 10, 22)

Secondary Outcome

Patient reported outcomes scores assessed with the Nijmegen Cochlear Implant Questionnaire (NCIQ), The Tinnitus Handicap Inventory (THI) and Dizziness Handicap Inventory (DHI). (18, 20, 24)

Third Outcome

Listening effort assessed with pupil dilation with HINT.(10)

Statistics

Power calculation

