Power calculations with a power of 0.8 with a significance level of 0.05 have been made with STATA IC-15 using standard deviations for the HINT test and expected effect size (38) the NCIQ(18), and the SSQ (internal communication with BEAR (Better Hearing Rehabilitation) study on hearing aid use in Denmark) (Table 1). An estimated within participant standard deviation from the BEAR study of 1,9 in an HA population using the

SSQ-12 is used to calculate the sample size. A difference of 1.4 will require 30 participants in each arm. The effect size is expected to be larger in the CI group which will lower the number of required subjects even further.

Based on this, 30 participants must be enrolled in each arm. Additional six patients (20%) in each arm will be enrolled in the study to account for dropouts.

Test	SD pre	SD post	Expected difference between the two treatment arms	Minimum required group size
1. HINT	6.3%	6.3%	5%	26
2. NCIQ – basic sound perception	14.4	23.5	53	4
2. NCIQ	13.4	19.6	34	6
2. NCIQ – speech perception	18.8	17.8	17	20
2.NCIQ Self-esteem	20.1	16.4	22	13
2.NCIQ Activity	23.0	15.9	27	10
2.NCIQ Social Interactions	19.8	14.5	25	9
3. SSQ Total	1.9	1.9	1.4	30

Table 1: Power calculations for the desired tests. Estimated within participant standard deviations (SD pre and SD post) with expected difference and the calculated required group size.

Definition of Analysis Sets

Strategy for intention to treat analysis with incomplete observations.(39)

1. Attempt to follow-up on all randomised participants, even if they withdraw from allocated treatment.
2. Perform a main analysis of all observed data that are valid under a plausible assumption about the missing data.
3. Perform sensitivity analyses to explore the effect of deviations from the assumption made in the main analysis.
4. Account for all randomised participants, at least in the sensitivity analyses.

Analysis specification

A constrained linear mixed model is used to analyse the outcome.

The model will include randomisation group (CI+HA / HA+HA) and time (baseline/follow-up) and their interaction as fixed effects along with the threshold strata that were used in stratifying the randomisation. The model is constrained so that the mean at baseline agrees across the two treatment groups adjusted for threshold stratum, which is reasonable due to the randomisation of implant fitting. Patient ID will be included as a random effect to account for the repeated measurements.

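### HINT, DANTALE I and SSQ-12 are all primary, but no rule says which results make the trial positive or how the 0.05 is controlled across them

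*SAP*

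**What the plan says.** Three places name the same primary set.

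- SAP, Primary Outcome: "Primary outcomes are Speech intelligibility scores measured objectively with HINT (sentences and words) and DANTALE I and subjectively with Speech, Spatial", going on to complete the name of the SSQ-12.
- Protocol, Abstract: "The primary outcome measures are Speech intelligibility measured objectively with HINT (sentences in noise) and DANTALE I (words) and subjectively", followed by the SSQ-12.
- Protocol, Primary Outcome: "Primary outcomes are Speech intelligibility scores measured objectively with HINT (sentences and words) and DANTALE I", again with the SSQ-12.

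The SAP hypothesis is that CI+HA patients "have increased objective and subjective measured speech intelligibility" compared with HA+HA patients. The first objective, in both documents, counts HINT and DANTALE I as the objective measures and SSQ-12 as the subjective one.

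The SAP section on effect size gives one objective effect (HINT) and one subjective effect (SSQ-12). It has no DANTALE I line. It lists HINT in two listening conditions and CI+HA follow-up at 3, 6 and 12 months, against a single HA+HA follow-up.

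The only error rate is in the protocol's Power calculation: "Power calculations with a power of 0.8 with a significance level of 0.05". There each outcome is sized alone. Table 1 gives HINT 26 per arm. For SSQ-12 the text says "A difference of 1.4 will require 30 participants in each arm". Table 1 has no DANTALE I row. The Analysis specification describes one type of model and says nothing about combining results across outcomes. The Sensitivity analysis section refers to a single main outcome and does not identify it.

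**The concern.** With three primary instruments and one alpha, the plan has to say what pattern of results supports the hypothesis. It does not. Suppose HINT and SSQ-12 are significant and DANTALE I is not, or DANTALE I and SSQ-12 are significant and HINT is not. The documents give no verdict in either case, so the same data could be called positive or negative after they are seen. The trial is open-label, one primary outcome is self-reported, and the stated purpose is to guide decisions on CI candidacy, so this affects the main conclusion.

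Two quantities are at stake: the chance of a false claim if any one success counts, and the power for the full claim if more than one success is needed.

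**Working it through.** **Inputs.** From Table 1 and the power text: HINT SD 6.3, difference 5; SSQ-12 SD 1.9, difference 1.4; alpha 0.05, power 0.8. Sidedness is not stated; two-sided is used because it reproduces the table. The documents give no correlation between outcomes, so 0, 0.5 and 0.8 are assumed.

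**1. The plan's own sizes.** The normal formula is n per arm = 2(1.960 + 0.842)² (SD/difference)².
- SSQ-12: 15.70 × (1.9/1.4)² = 28.9.
- HINT: 15.70 × (6.3/5)² = 24.9.

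The t-based solution gives 29.90 and 25.92, that is 30 and 26 per arm, exactly as in Table 1. The sample-size arithmetic is not at fault.

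**2. If any one success counts.** For K independent tests the error is 1 − 0.95^K: 1 − 0.95² = 9.75% and 1 − 0.95³ = 14.26%. For equal correlation r > 0 it is 1 − ∫ φ(u) [Φ((1.96 − √r·u)/√(1−r)) − Φ((−1.96 − √r·u)/√(1−r))]^K du.

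| Tests at two-sided 0.05 | r = 0 | r = 0.5 | r = 0.8 |
|---|---|---|---|
| HINT, DANTALE I, SSQ-12 | 14.3% | 12.5% | 9.8% |
| HINT and SSQ-12 only | 9.8% | 9.1% | 7.8% |

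Counting only false claims in favour of CI+HA, the three-instrument figures are 7.3%, 6.3% and 4.9%, against 2.5% for one test.

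**3. If both domains must succeed.** If objective means HINT alone, a false joint claim requires a false HINT result (or a false SSQ-12 result), so its chance cannot exceed 5%. Requiring HINT and DANTALE I together is stricter still. If HINT or DANTALE I may satisfy the objective part, the bound is lost. Take no true effect on either, and SSQ-12 truly at 80% power. At r = 0 the false-claim rate is 0.0975 × 0.80 = 7.8%. Simulated t-tests at 30 per arm give about 8%, 6% and 4% at r = 0, 0.5 and 0.8 (two-sided). The excess over 5% therefore disappears at high correlation.

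**4. Joint power for HINT and SSQ-12.** The noncentrality is (difference/SD)√(n/2). At 30 analysed per arm this is 0.794 × 3.873 = 3.07 for HINT and 0.737 × 3.873 = 2.85 for SSQ-12, giving 85.6% and 80.1% singly. At r = 0 the joint power is 0.856 × 0.801 = 68.6%.

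The planned mixed model also uses the baseline. If Table 1's SDs are cross-sectional, the effective SD is SD × √(1 − ρ²), where ρ is the baseline/follow-up correlation (assumed). At ρ = 0.5 the factor is 0.866, single powers become 93.7% and 90.0%, and 0.937 × 0.900 = 84.3%.

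| 30 analysed per arm | r = 0 | r = 0.5 | r = 0.8 |
|---|---|---|---|
| Unadjusted t-test (reproduces Table 1) | 69% | 73% | 76% |
| Baseline used, ρ = 0.3 | 74% | 77% | 80% |
| Baseline used, ρ = 0.5 | 84% | 86% | 88% |

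If DANTALE I must succeed as well, these are upper bounds. Its own power cannot be computed, because no SD or difference is given.

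**The case against.** The strongest defence is that the plan already implies a rule. The hypothesis asks for objective and subjective gains, and the effect-size section names one effect for each. On that reading HINT and SSQ-12 are co-primary, both must succeed, and no alpha adjustment is needed. This is a natural reading, and it means that the 14.3% depends on a rule no passage states. It does not close the gap. The hypothesis names no test or criterion, and the first objective puts DANTALE I alongside HINT as objective. Step 3 shows that error control turns on which of these is meant.

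A reader might infer that the trial is underpowered under any rule. The documents do not support that. The 0.8 is given per outcome and no joint power is promised. Table 1 calls its SDs within-participant, yet lists separate pre and post values that differ for NCIQ (14.4 and 23.5 for basic sound perception), which looks like spread at each visit. If so, the planned model may bring joint power above 0.8.

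A reader might also infer that DANTALE I was left unclassified. It is classed as objective; what it lacks is a role in a success rule, an effect size and a sample-size row.

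Appendix A was not available for this review. Both documents describe it as a data description, so a decision rule is not expected there.

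**Conclusion.** The point stands and should be fixed before analysis. The omission is clear from the text: three primary instruments, one alpha and no decision rule. Its size depends on assumptions. Family-wise error is 9.8% to 14.3% for three instruments, or 7.8% to 9.8% for HINT and SSQ-12, if any one success at unadjusted 0.05 is claimed, over assumed correlations of 0.8 down to 0. Under a both-domains rule, error is controlled if objective is tied to one named test or to all objective tests. It reaches about 4% to 8% if either objective test may count and SSQ-12 has 80% power.

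A shortfall in joint power is possible but not established: the range at 30 analysed per arm is 69% to 88%, depending on what the Table 1 SDs represent and on two unstated correlations. It would be lower if fewer are analysed. The protocol plans for losses ("Additional six patients (20%) in each arm will be enrolled in the study to account for dropouts") and warns of them ("Possible large drop rates if new HAs improve speech intelligibility to an extent that CI treatment is rejected or postponed").

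**What to change.** Before any data are analysed, write one success rule into the SAP at overall two-sided 0.05, for one named listening condition and one named visit in each arm. Any of these would do:

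- **Co-primary:** HINT and SSQ-12 must both be significant at 0.05; DANTALE I is supportive.
- **Fixed sequence:** the three outcomes are tested at 0.05 in an order the sponsor chooses, stopping at the first failure.
- **Holm** over the three, with a statement of which rejections support the full hypothesis.

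State that the 0.8 in the protocol's Power calculation is per outcome. Give the power for the chosen rule as a range, with its SD and correlation assumptions. If DANTALE I is tested formally, add its effect measure, SD and expected difference. Treat other listening conditions and the 6- and 12-month results as supportive, and identify the main outcome in the Sensitivity analysis section.

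**Cost.** SAP wording only, with no change to data collection or sample size. Each rule has a price, shown here for the unadjusted t-test at 30 analysed per arm and outcome correlations of 0 to 0.5:

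- Co-primary: 69% to 73% for the full claim, against 80% to 86% for one outcome alone.
- Fixed sequence: the first outcome keeps its single-test power, but a later one cannot be claimed if an earlier one fails. With HINT and SSQ-12 in the first two places, in either order, the second has 69% to 73%. The third has about 55% to 64% if DANTALE I is assumed to have 80% alone (at r = 0, 0.686 × 0.80 = 0.549).
- Holm, same DANTALE I assumption: about 79% to 81% for HINT, 74% to 75% for SSQ-12, and 64.0% to 67.5% for both together.

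All these figures rise if the model gains precision from the baseline.

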REDCap will also be used to send out the questionnaires to the participants' online mailbox (called Eboks in Denmark) throughout the study (see timeline (Figure 2)) and automatically save the data.

Participants will have the opportunity to return to their original HAs if they prefer to do so after one-month of acclimatisation.

Control Group

Thirty patients, who will be age-matched, randomised and allocated to the control group HA+HA will continue the use of the new replacement HAs for another three months (total four months of new replacement HA+HA use), serving as the delayed intervention control group.

Intervention Group

Thirty patients, who will be age-matched, randomised and allocated to the intervention group CI+HA will undergo surgery as soon as possible after the HA acclimatisation period.

HA Fitting

The participant will receive either Phonak (Phonak Link M) or GN (ReSound LiNX Quattro or Resound ENZO Q) based on their personal preference. Both these HA models can be fitted with a CI by Advanced Bionics and Cochlear, respectively.

The HAs will be fitted according to NAL-NL2 procedures prescriptive fitting formula, which optimizes audibility in the bimodal solution(2) and will be verified with REM (Real Ear Measurement) to ensure that the HA is providing adequate gain and then further adjusted for comfort based on patient feedback.(35)

The new HAs will be prescribed to the patients free of charge and future service will also be free of charge.

Participants can drop out of the study if they do not want CI surgery. Collected data will be analysed if the patient still consents.

CI fitting

The CI will be selected depending on the participant's HA selection; that is, the CI that is compatible with the HA will be selected in order to ensure the most optimal bimodal fitting. One-month post-surgery, the CI will be activated according to the settings and stimulation strategy based on patient's feedback. The CI will then be fitted with the HA according to the bimodal fitting formula allowing the HA to keep the NAL-NL2 fitting along with the wireless connection with the CI. (36, 37)

Patients hearing thresholds will be tested on CI activation day. The residual hearing will not be stimulated in this study.

All participants are offered standard rehabilitation with a speech therapist, including three visits a week up to 10 weeks following the initial fitting.

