Secondary outcomes will be analysed analogously in a constrained linear mixed model adjusting for randomisation strata. Model validation checks will be undertaken as described above, switching to bootstrapping the standard errors when model assumptions are rejected.

Covariates such as age and gender will be included in all models.

Sensitivity analysis

Inclusion is performed conditional on Pure Tone Average (PTA) (from 0.5 to 4 kHz) $PTA > 40 \text{ dB HL}$ and SIS $<50\%$ in the ear considered for CI implantation and $<70\%$ in the best-aided condition which may lead to a truncation effect in the distribution of baseline measurements. To address this, an analysis of covariance (ANCOVA) model conditioning on the baseline will be used to obtain a sensitivity analysis estimate for the main outcome.(40)

The statistical analysis plan is attached as “supplementary file” along with the Data Description listed in Appendix A.

Patient and Public Involvement

A focus-group interview was established with six cochlear implant patients. The patients commented on their decision to transition from HA to CI. Based on the feedback from the focus group, the research questions were developed.

The patients also reported problems with adjustments of the CI, when meeting the audiologist for CI adjustment controls.

Ethics and Dissemination

Ethics approval for the conduct of this study was obtained from the Ethics Committee Southern Denmark, 21st August 2020 project ID S-20200074G.

The project is approved by the Danish Data Protection Agency (file no. 20/22868) in Region South Denmark.

All participants are treated according to current clinical standards regardless of the randomised study participation. The participants are volunteers and can at any moment withdraw their participation in the study without affecting their current or future treatment rights.

The Informed Consent form will be found online as an online supplementary file and it will be signed by all participants willing to participate the study and stored in their electronic journals in Department of Audiology, Odense University Hospital. All patients are given both oral and written information about the study.

Results

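### As ordinarily fitted, the patient random effect assumes equal SDs at baseline and follow-up. Table 1's NCIQ SDs differ, so NCIQ intervals can be too narrow or too wide, and the checks behind the bootstrap are not described.

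*SAP*

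**What the plan says.** The Analysis specification (SAP section 3, repeated in the Protocol) describes a constrained linear mixed model with group, "time (baseline/follow-up) and their interaction as fixed effects along with the threshold strata". On covariance it adds only that "Patient ID will be included as a random effect to account for the repeated measurements". It states no residual structure, no visit-specific variance and no robust standard error as default.

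NCIQ, THI and DHI use the same model: "Secondary outcomes will be analysed analogously in a constrained linear mixed model adjusting for randomisation strata". The one safeguard follows: "Model validation checks will be undertaken as described above, switching to bootstrapping the standard errors when model assumptions are rejected". Nothing before that sentence, in either document, describes a check, a rejection rule or a resampling unit. The ANCOVA sensitivity analysis covers only the main outcome and addresses baseline truncation.

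Table 1 of the Protocol gives an SD pre and an SD post for each scale, with the caption "Estimated within participant standard deviations (SD pre and SD post) with expected difference and the calculated required group size". Its difference column is headed "Expected difference between the two treatment arms".

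On visits, the SAP defines the subjective effect as "Mean difference in SSQ-12-scores at 3, 6 and 12 months follow-up post- bimodal CI+HA-fitting and 3 months post-HA-fitting respectively", and the HINT effect on the same schedule. No schedule is stated for NCIQ.

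**The concern.** A random intercept with a single residual variance gives every visit the same variance. The treatment effect is read at follow-up. If the follow-up variance differs from baseline, pooling the two gives the effect a standard error that belongs to neither.

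The sponsor's own planning figures say the variances differ for most NCIQ scales, upwards in two rows and downwards in three. NCIQ carries the second objective, so its intervals will be reported. Whether the bootstrap corrects them depends on a check that has not been written down.

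**Working it through.** **Inputs.** SDs, differences and group sizes are from Table 1; 30 per arm, 80% power and 5% significance are from the Power calculation. The correlation between visits is not given, so 0.3 to 0.7 is assumed.

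**Reproducing Table 1.** A two-sample t-test with unequal SDs (two-sided 5%, 80% power) gives 26, 4, 6, 20, 12, 10, 9, 30 per group. The table has 26, 4, 6, 20, 13, 10, 9, 30. Only self-esteem differs, by one. The table therefore uses its SDs as ordinary between-patient SDs, despite the within-participant caption. The same is assumed here.

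**One follow-up.** Write a for SD pre and b for SD post. The random-intercept fit estimates one pooled variance v and one pooled covariance c. The effect is the follow-up difference minus w times the baseline difference, with w = c/v.

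- *SD post in the implanted arm only.* v = (3a² + b²)/4. Model variance = (2/n)·v·(1 − w²). True variance = (1/n)·(a² + b²)·(1 − w²). Ratio = (3a² + b²) / [2(a² + b²)].
- *SD post in both arms.* v = (a² + b²)/2. True variance = (2/n)·b²·(1 − w²). Ratio = (a² + b²) / (2b²).

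Neither ratio contains the correlation or n, so enrolling 36 per arm instead of 30 does not help. With r the square root of the ratio, the type I error is 2[1 − Φ(1.96 r)], which is also the non-coverage of a nominal 95% interval.

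Basic sound perception, implanted arm only: (3·207.36 + 552.25) / (2·759.61) = 1174.33/1519.22 = 0.773, so r = 0.879 and the error is 8.5%. Activity: (3·529 + 252.81) / (2·781.81) = 1839.81/1563.62 = 1.177, so r = 1.085 and the error is 3.4%.

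| Table 1 row | SD pre / post | Larger ÷ smaller | r, implanted arm only | Error | r, both arms | Error |
|---|---|---|---|---|---|---|
| Basic sound perception | 14.4 / 23.5 | 1.63 | 0.879 | 8.5% | 0.829 | 10.4% |
| NCIQ, no subdomain named | 13.4 / 19.6 | 1.46 | 0.905 | 7.6% | 0.857 | 9.3% |
| Speech perception | 18.8 / 17.8 | 1.06 | 1.014 | 4.7% | 1.028 | 4.4% |
| Self-esteem | 20.1 / 16.4 | 1.23 | 1.049 | 4.0% | 1.119 | 2.8% |
| Social interactions | 19.8 / 14.5 | 1.37 | 1.073 | 3.6% | 1.197 | 1.9% |
| Activity | 23.0 / 15.9 | 1.45 | 1.085 | 3.4% | 1.243 | 1.5% |
| HINT; SSQ total | equal | 1.00 | 1.000 | 5.0% | 1.000 | 5.0% |

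REML simulation at 30 per arm agrees: with SD post in the implanted arm only, 8.3 to 8.7% for basic sound perception and 3.4 to 3.6% for activity.

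**In points on the scale** (implanted arm only, correlation 0.5, t with 58 df). Basic sound perception: the interval half-width is 7.8 where 8.9 is needed, so coverage is about 91.5%. Activity: 9.7 against 8.9, too wide. The planned 27-point activity difference is still about 5.6 model standard errors.

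**Three implanted-arm visits, one control visit** (large-sample calculation, equal correlation between all visits, SD post at every implanted-arm follow-up).

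- *Implanted arm only, visits modelled separately, 3-month contrast:* 5.0 to 5.5% in every row.
- *Implanted arm only, all three visits coded as one follow-up level:* the direction reverses, with about 3.5 to 4.8% for basic sound perception and 6.5 to 6.7% for activity.
- *SD post in both arms:* distortion persists in every layout, about 8 to 10% for basic sound perception.

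**The safeguard** (simulation, one follow-up, implanted arm only, correlation 0.5). If the unstated check is a Shapiro-Wilk test, the bootstrap is triggered in 5 to 22% of trials and basic sound perception stays at 7.8%. If it compares variances between visits in the implanted arm, it is triggered in 85% of trials for that row and the error falls to 5.6%.

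**The case against.** The strongest reply is that the harm depends on a layout the SAP does not clearly specify. If NCIQ follows the 3, 6 and 12-month schedule with visits modelled separately, and only implanted patients take SD post, almost nothing is wrong. That stands. It is why no single direction or size can be claimed.

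A reader might infer that SD post must belong to the implanted arm only, because controls "will continue the use of the new replacement HAs for another three months" and because the group sizes reproduce. The first is a reasonable argument. The second is not evidence, because with equal groups the sample-size formula is symmetric in the two SDs. The documents do not say which arm has SD post.

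A reader might also infer that the plan prescribes equal variances. It does not; visit-specific variances are not excluded. The objection is to the ordinary fit of what is written, and to leaving the choice open.

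Finally, a safeguard exists, and with a suitable check it works nearly as well as an unconditional bootstrap (4.4 to 6.5% against 5.0 to 6.2% in the five affected rows). That also stands, but the plan does not name such a check.

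**Conclusion.** The point holds as a minor one. On the plan's own planning SDs, the ordinary fit mis-sizes NCIQ standard errors under most readings of the visit layout and of which arm has SD post. The error can go either way.

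It would be wrong to conclude that NCIQ intervals will be too narrow, or that the primary results are in doubt. In the one-follow-up layout three of the five affected rows err on the conservative side. HINT and SSQ-12 have equal planning SDs, and the planned NCIQ effects would still be detected. DANTALE I, THI and DHI have no row in Table 1, so nothing is claimed for them. What is at stake is the width and coverage of NCIQ intervals, and any NCIQ scale whose effect is smaller than planned.

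The figures assume that Table 1's SDs are between-patient SDs and will hold in this trial, that data are normal and complete, and that strata and covariates are left out.

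**What to change.** For the NCIQ analyses, do one of the following.

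- Let variances differ by visit, and by arm at follow-up: an unstructured covariance with Satterthwaite or Kenward-Roger degrees of freedom.
- Use patient-level robust or bootstrap standard errors from the start, not conditionally on a check.

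With one follow-up and SD post in the implanted arm only, simulated type I error in the five affected rows is 4.6 to 4.9% for the unstructured form with arm-specific follow-up variance, 5.0 to 5.5% for robust and 5.0 to 6.2% for bootstrap standard errors.

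The NCIQ follow-up visits and their coding in the time factor should be stated too. As a clarification, replace the reference to checks described earlier with the checks themselves, including equality of variance across visits and arms, and name the patient as the resampling unit.

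The cost is a few sentences in the SAP. With one follow-up there is one more covariance parameter (3 instead of 2), or three more (5) if the follow-up variance and covariance are arm-specific. Where variances are equal the loss of precision is about 1% (HINT, correlation 0.5: SD of the estimated effect 1.42 against 1.41). Robust and bootstrap standard errors are slightly too small at 30 per arm. With several visits the unstructured fit may not converge, so robust standard errors should be named as the fallback.
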